## JHM IRB - eForm A – Protocol

- Use the section headings to write the JHM IRB eForm A, inserting the appropriate material in each. If a section is not applicable, leave heading in and insert N/A.
- When submitting JHM IRB eForm A (new or revised), enter the date submitted to the field at the top of JHM IRB eForm A.

\*\*\*\*\*

### 1. Abstract

- a. Provide no more than a one page research abstract briefly stating the problem, the research hypothesis, and the importance of the research.

Chronic neck and back pain has become one of the leading causes of disability and loss of productivity. For many patients with facet- or sacroiliac joint-mediated pain who have responded to diagnostic nerve blocks, radiofrequency ablation of the nerves innervating the joints can provide long-term relief. Radiofrequency ablation (RFA) is a relatively safe procedure with minimal risk of adverse events. However, with any procedure involving damage to the peripheral nervous system, there is risk of post-procedure neuropathic pain. Following both lumbar facet joint RFA, and sacroiliac joint RFA, post-ablation neuropathic pain (PAN) has been documented at a rate ranging from 0.5% to 9.2% per lesion, and can last several weeks, resulting in a decrease in quality of life during this time period.

Transforaminal epidural and intra-articular steroid injections are commonly used in interventional spine procedures to decrease the inflammation at the nerve root or the facets, and pain relief. Therefore, we will test the hypothesis that dexamethasone injection delivered at the time of lesion effectively prevents the development of PAN through a placebo-controlled, double-blind, randomized, multi-center trial in patients undergoing cervical, thoracic, lumbar, and sacroiliac joint radiofrequency denervations.

### 2. Objectives (include all primary and secondary objectives)

- Primary: To determine if the immediate administration of dexamethasone to the post-ablation site diminishes the incidence of post-ablation neuropathic pain
- Secondary: Stratify cervical vs. thoracic vs. lumbosacral data points to compare if post-ablation neuritis is dictated by anatomical location. Also look at the gauge of the needle used in each patient and radiofrequency parameters to see if associated with neuritis incidence. We will track level of disability and effectiveness of ablations with completion of Oswetry Disability Index and/or Neck Disability Index at baseline, 4 weeks, and 8 weeks after completion of bilateral ablations.

**3. Background** (briefly describe pre-clinical and clinical data, current experience with procedures, drug or device, and any other relevant information to justify the research)

Chronic neck and back pain has become one of the leading causes of disability and loss of productivity. This is often associated with poor quality of life, depression, anxiety, and sleep disorders. Conservative measures, such as physical therapy and medications are first-line treatment options and provide improvement of pain in some patients. However, for those who are not responsive to conservative management, interventional procedures are another treatment option. For many patients with facet- or sacroiliac joint-mediated pain who have responded to diagnostic nerve blocks, radiofrequency ablation of the nerve innervating the joints can provide long-term relief. Radiofrequency ablation (RFA) is a relatively safe procedure with minimal risk of adverse events.[1] However, with any procedure involving damage to the peripheral nervous system, there is risk of post-procedure neuropathic pain. Following both lumbar facet joint RFA, and sacroiliac joint RFA, PAN has been documented at a rate ranging from 0.5% to 9.2% per lesion. [2]

PAN is described as a burning pain at the level of the ablation. In patients who have undergone lumbar facet or sacroiliac joint radiofrequency denervation, these symptoms can last anywhere from 2 to 6 weeks. [2,3] Unfortunately, the incidence of PAN is higher in patients who have undergone cervical facet radiofrequency innervation. The incidence is reported to be approximately 19 percent, with an average duration of 2.6 months [4] and can drastically affect a patient's quality of life during this time period.

Transforaminal epidural and intra-articular steroid injections are commonly used in interventional spine procedures to decrease the inflammation at the nerve root or the facets, and pain relief. Therefore, we will test the hypothesis that steroid injection delivered at the time of lesion effectively prevents the development of PAN through a placebo-controlled, double-blind, randomized trial in patients undergoing cervical, thoracic, lumbar, and sacroiliac joint radiofrequency denervations.

### **Study Procedures**

a. Study design, including the sequence and timing of study procedures (distinguish research procedures from those that are part of routine care).

This is a multi-centered double-blinded prospective clinical trial. Patients will be recruited from the pool of patients seen by [name] in the pain management clinic through the Department of Physical Medicine and Rehabilitation. Patients will be recruited from the pools of patients seen by PIs at our collaborating sites (Cornell/Columbia) in the pain management clinic through the Department of Physical Medicine and Rehabilitation. Candidacy for bilateral ablation will be determined by the standard of care, mainly pain relief >50% after two prior bilateral diagnostic blocks. In routine care, these patients are seen in clinic to discuss the risks and benefits of radiofrequency ablation in a clinic. Once patients are consented, they are brought in for the procedure in 2 to 4 weeks. Patients who were not consented in the clinic will also have the opportunity to enroll in the study on the day of their

procedure. They first receive a unilateral lesion, and are brought back to receive a lesion on the other side in no sooner than one week. Patients will then be followed in the clinic in 4 weeks after the procedure to monitor response. Patients can request an earlier appointment if complications arise. If patients develop PAN, they are either monitored without intervention, or initiated on gabapentin or oral corticosteroids, depending on the severity of their symptoms.

- b. In this multi-center study, Johns Hopkins will be the coordinating center. All contributing PIs from our collaborating sites have provided contact information (email, direct phone numbers, and addresses of their respective offices). Each center will be submitting separate IRB protocols at their respective institutions. Once approved they will send us copies of completed documents and consent forms. Although this research is not federally funded (as mentioned later in this protocol) all participating centers will file an FWA with OHRP. Any changes to the protocol will be communicated between sites via secured email to assure all sites have the most current version of the protocol. Data will be collected at each respective site and stored on encrypted servers. The collected data will be shared once enrollment is complete for analytical purposes only. If any events or deviations occur at participating centers, our collaborating PIs have agreed to notify the coordinating center (Johns Hopkins) immediately so we may act in a timely fashion.

In our study, we will add the following steps:

- Patients will also be consented for the study at the same time as the time of consent for radiofrequency ablation. If patients choose not to participate, they will continue with routine care.
- At the time of the unilateral lesion, either steroid (dexamethasone 4mg/mL, with 1mL given at each lesion site) or normal saline (1mL) will be administered at the lesion site as determined by randomization.
- At the time of lesion on the other side, steroid will be administered at the lesion site if normal saline was given previously on the opposite side, and vice versa,
- There will be an initial 2 week follow up asking exclusively about development of post-ablation neuropathic pain. At the two post-procedure visits spaced 4 weeks apart, patients will be given a questionnaire that will ask about development of neuritis, and any adverse reactions after the procedure. If neuritis is present, the onset and duration will also be recorded. If neuritis is present, but the level is generalized or unclear, post-ablation neuritis will be recorded at a single level that most closely matches the clinical presentation. The questionnaire will then be scanned into the patient chart, and reviewed by co-investigators when data collection occurs. Repeat ODI and/or NDI will be filled out at these follow ups to track efficacy of ablations. If patients cannot be seen in clinic at the 4 week or 8 week follow up, co-researchers will follow up with patients by phone.

- c. Study duration and number of study visits required of research participants.

- Patients will be enrolled in the study for approximately 3 months, and will be seen at a total of 4 visits - 1 pre-ablation visit 1 month prior to the procedure, for the procedure itself, and post-ablation for 2 visits spaced 4 weeks apart. There is also a 2 week telephone follow up exclusively assessing incidence of PAN. The study itself will take place over a period of 2 years in order to enroll enough patients to have an adequately powered study.
- d. Blinding, including justification for blinding or not blinding the trial, if applicable.
  - This trial will be double blinded to ensure that there is no bias on the part of the provider performing the procedure or seeing the patient in follow up, or on the part of the patient when reporting outcomes
  - Patient is seen in clinic by either the nurse practitioner, fellow, resident, or [name] (the same applies to collaborating sites and respective PIs) and is identified as needing bilateral ablations of the cervical, thoracic, or lumbar facets, or sacroiliac joints, and is consented for the study.
  - As part of routine care, the provider that saw the patient then notifies the secretary of the procedure that is needed. Information will also be included that the patient is eligible for the study. Subsequently, the secretary will call the patient to set up procedure dates. The same process is to be conducted at our collaborating sites.
  - The procedure schedule will be sent to [name] (or respective collaborating PIs) and the research team members the night before procedure day with the scheduled patients. Patients in the study will be marked on this schedule.
  - The research team adds the eligible patients to a separate list that is sent to an un-blinded co-investigator with directions on which side to inject dexamethasone or normal saline based on randomization
- e. Justification of why participants will not receive routine care or will have current therapy stopped:
  - Not applicable. All patients in this study will continue to receive routine care, through scheduled ablation procedure and continuation of established medication regimen for pain management.
- f. Justification for inclusion of a placebo or non-treatment group.
  - A placebo group is present to compare the current standard of care and the addition of our intervention and to ensure that any changes are the not the result of the experimental paradigm (i.e. active injection post-lesion).
- g. Definition of treatment failure or participant removal criteria.
  - Treatment failure is defined as the presence of post-ablation neuropathic pain in the period up to 2 months after post-ablation steroid administration.
  - Participant removal criteria:
    - at patient request for removal

- development of immediate onset of weakness or sensory changes post-injection. At that point, the patient will not be given further injections, but data will be used to report an adverse event
- lack of post-procedure follow up
- Any additional procedures that include additional steroid administration

h. Description of what happens to participants receiving therapy when study ends or if a participant's participation in the study ends prematurely.

- Patients will continue with routine care when the study ends or if their participation in the study ends prematurely. They will be continued to be followed at the pain clinic, and if determined to need subsequent radiofrequency ablations after the participation in the study, these will be done routinely without administration of post-ablation dexamethasone or normal saline.

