## 7. Risks

- a. Medical risks, listing all procedures, their major and minor risks and expected frequency.
  - Radiofrequency ablation of cervical, lumbar, or thoracic facets or sacroiliac joint

- major risks: dural puncture, spinal cord injury, hematoma formation, infection. These are exceedingly rare with no cases reported in the literature to date. [5]
- minor risks: pain at injection site (0.5% frequency), and neuritis (0.5% to 19%), vasovagal reaction (1%)[3,6]
- Administration of steroids at the lesion site
  - major risks: infection, spinal cord injury are exceedingly rare. Reports are limited to a few case studies. In a large study by El-Yahchouchi et al. in 2016, showed with no reported incidences.
  - minor risks: flushing, headaches (2.6%). [7], increased blood glucose
- b. Steps taken to minimize the risks.
  - the procedure will be performed in a sterile fashion under fluoroscopic guidance to decrease the risk of infection, spinal cord injury, and dural puncture. Patients who are anticoagulated will not undergo the procedure. Only non-particulate steroids, such as dexamethasone, will be used to decrease the risk of spinal cord injury.
- c. Plan for reporting unanticipated problems or study deviations.
  - any unanticipated problems or study deviations will be reported immediately to the PI, who will then notify the IRB. Enrollment in the study will be stopped at that point until adjustments to the protocol can be made.
- d. Legal risks such as the risks that would be associated with breach of confidentiality.
  - As the proposed study does not involve collection or usage of information regarding sensitive materials, such as alcohol or drug use, illegal activities, sexual activity, or mental illness, potential breach of confidentiality does not pose large legal or societal risks. Patients will be de-identified through the assignment of subject ID numbers. The study team will take strong precautions to prevent any possibility of such breach by storing all data on encrypted servers and storing all hard copies of patient sensitive materials in the PIs' offices
- e. Financial risks to the participants: none

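### Scheduled adverse-reaction questions start only after both agents have been given and no onset date is specified, so the named systemic steroid effects cannot be reliably attributed to dexamethasone or saline

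*Combined protocol and SAP*

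**What the plan says.** All references are to the combined protocol and SAP.

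- **First contact.** Study Procedures, item b: "There will be an initial 2 week follow up asking exclusively about development of post-ablation neuropathic pain". Item c repeats the restriction for the telephone call.
- **First adverse-reaction question.** At the two later post-procedure visits, item b says "patients will be given a questionnaire that will ask about development of neuritis, and any adverse reactions after the procedure".
- **Timing of those visits.** Item b adds "Repeat ODI and/or NDI will be filled out at these follow ups to track efficacy of ablations". Section 2 dates the same disability indices "at baseline, 4 weeks, and 8 weeks after completion of bilateral ablations".
- **Gap between sides.** Study Procedures, item a: patients "are brought back to receive a lesion on the other side in no sooner than one week". No maximum is given. Item b assigns the second side whichever agent the first side did not receive.
- **Dating of events.** Item b asks for onset and duration of neuritis. It says nothing on this for other reactions.
- **Named steroid harms.** Section 7, item a: "minor risks: flushing, headaches (2.6%). [7], increased blood glucose". It also lists infection and spinal cord injury as major but very rare risks.
- **Other routes of capture.** Patients may ask for an earlier appointment (Study Procedures, item a). Sites notify the coordinating center of events at once (item b). Immediate weakness or sensory change stops further injections and is reported (item g). Unanticipated problems go at once to the PI and then to the IRB (Section 7, item c).
- **Analysis.** Section 6 lists no safety outcome and no comparison of adverse reactions.

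**The concern.** The design compares one side of a patient with the other. That works for post-ablation neuropathic pain (PAN), which has a location. It does not work for a headache, a flush or a raised glucose reading, because these belong to the whole patient. Only timing can link them to one injection. If nobody asks until both agents have been given, and no date is called for, that link depends on memory and on what happens to be written down.

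Three things are at stake. The trial adds a drug to routine care and has a saline control, but on the stated schedule it gains little from that control for these effects. Short-lived minor reactions recalled after a month or more are likely to be under-reported. The second injection can also be given without any structured question about the first.

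**Working it through.** The protocol gives no figure of its own to reproduce here. The check traces the schedule, followed by some simple arithmetic.

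**1. When adverse reactions are first asked about.** Inputs: minimum gap between sides 7 days (Study Procedures, item a); first visit with the adverse-reaction question 28 days after completion of both sides (Section 2, linked to item b through the disability indices).

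- From the second injection: 28 days.
- From the first injection: gap + 28 days. At the minimum gap, 7 + 28 = 35 days. Because no maximum is stated, the figure rises with the gap: 14 + 28 = 42 days for a two-week gap, 28 + 28 = 56 days for a four-week gap.

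**2. What the patient has received by then.** A patient who completed both sides has had one injection of each agent.

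**3. Whether each named steroid harm can be assigned from what is planned.**

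- Flushing, headache, raised blood glucose: no side, and no onset date specified. Not reliably assignable.
- Infection: can be localised to the treated side.
- Spinal cord injury: would probably appear as the immediate weakness or sensory change that item g ties to a given injection.

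So three of the five named harms lack a planned means of assignment.

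**4. Whether the reading of the visit dates matters.** Item a speaks of clinic follow-up 4 weeks after the procedure without saying which one. If that meant the first procedure, the adverse-reaction question would come 28 days after the first injection. With the second side treated at 7 days, it would still come 28 − 7 = 21 days after the second. Only a gap of more than 4 weeks would put the question before the second injection, and item b schedules no follow-up visit between the two. The protocol also does not say which procedure the 2-week contact follows. On either reading, that contact asks about PAN alone.

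**5. Illustrative size.** Inputs: 2.6% headache (Section 7); 366 patients (Section 6). Assumptions: the rate applies once per patient, and half the patients receive dexamethasone first.

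- Expected patients with headache: 0.026 × 366 = 9.5.
- First-injection groups: 366 / 2 = 183 each.
- Expected headaches in the steroid-first group after that injection: 0.026 × 183 = 4.8.
- Even a split of 5 v 0 gives a two-sided Fisher p of 2 × (183 × 182 × 181 × 180 × 179) / (366 × 365 × 364 × 363 × 362) ≈ 0.06.

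A first-injection comparison would therefore describe the reactions; it would not be a powered test.

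**The case against.** The strongest reply has five parts.

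- **Other routes exist.** Patient-requested appointments, immediate site notification, the report to the PI and IRB, and the immediate weakness or sensory change rule can all yield dated events. This stands as a limit on the point. However, the last rule covers only neurological events. The other routes depend on someone volunteering a complaint, and none asks about flushing, headache or glucose. Volunteered reports are a poor basis for comparing rates between agents.
- **The questionnaire form is not in the documents.** It may contain a date field. This also stands: what can be said is that onset is not specified for these reactions, not that it goes unrecorded. A date field would still leave recall of at least 4 weeks and no question before the second injection.
- **Comparative safety is not a stated aim.** Sections 2 and 6 list no safety objective, and Section 5 relies on a known safety profile. Correct, and this is why the point does not touch the primary analysis. Adverse reactions are being collected all the same, and the present form makes them hard to interpret.
- **The 2.6% may not transfer.** By its title, the cited source concerns epidural steroid injections, and no saline background rate is given. The count of 9.5 is an illustration only.
- **Asking could unblind.** A report of flushing before the second injection may suggest which side had steroid, before the patient-reported primary outcome is complete. This is a real cost and has to be managed.

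A reader might infer that no named steroid harm can be attributed in any patient. The documents do not support that: infection can be localised, immediate neurological change is tied to an injection, and a patient stopped after such a reaction to the first injection has not had both agents.

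**Conclusion.** The point holds for the systemic effects. On the stated schedule, planned questions on adverse reactions begin 28 days after the second injection and at least 35 days after the first. By then, patients who completed both sides have had both agents, and onset is specified for neuritis only. Flushing, headache and raised blood glucose therefore cannot be reliably attributed to dexamethasone or saline.

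This rests on reading the two post-procedure visits as the 4- and 8-week assessments dated in Section 2, and on the protocol's silence about onset, since the form itself was not available. It would be too strong to infer that attribution is impossible, because unsolicited reports between the procedures could carry a date.

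The size is modest: about 9.5 of 366 patients with headache if 2.6% applies once per patient. The change is worth making because it is cheap. Leaving it out would not invalidate the PAN comparison.

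**What to change.** In Study Procedures, items b and c, remove the word that confines the 2-week contact to PAN. Ask the same short adverse-reaction question, with onset date, at:

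1. the second-procedure visit, before the second injection;
2. the 2-week contact, stating which procedure it follows;
3. the 4- and 8-week visits.

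In Section 6, state that reactions will be tabulated descriptively by the injection that they followed. The first-injection comparison (about 183 v 183 if the order splits equally) should be shown separately, because those patients have had only one agent. No hypothesis test is needed.

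To protect the blind, have the answers collected by an existing team member who does not assess PAN, and keep them from the PAN assessor. The un-blinded co-investigator already in the plan could do this, with fixed wording so that knowledge of allocation does not shape the questions.

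**Cost.** A few questions and one date field at contacts already planned, with no added visit or test. The contacts become slightly longer. Some risk remains that a reaction such as flushing hints at allocation; separate collection limits this for the assessor but cannot remove it for the patient.

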#### **5. Drugs/ Substances/ Devices**

a. The rationale for choosing the drug and dose or for choosing the device to be used.

- Dexamethasone is a well-known anti-inflammatory medication that is often used in transforaminal epidural steroid injections and intra-articular facet injections. The dose of dexamethasone is 4mg/mL, with 1 mL given at each level. PAN is caused by inflammation due to the nature of the procedure. The rationale behind dexamethasone pre-treatment is that the inflammatory response would be blunted and subsequent pain would be reduced or eliminated.

b. Justification and safety information if FDA approved drugs will be administered for non-FDA approved indications or if doses or routes of administration or participant populations are changed.

- Dexamethasone has a well-known safety profile. The medication will be used at doses that are currently used in routine spinal corticosteroid injection procedures. The only difference is that the dose will be given after radiofrequency ablation at each lesion site.
- c. Justification and safety information if non-FDA approved drugs without an IND will be administered.: N/A

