## 6. Study Statistics

- a. Primary outcome variable.
  - Presence of post-ablation neuritis at each lesion site
- b. Secondary outcome variables: none
- c. Statistical plan including sample size justification and interim data analysis.
  - A McNemar's Test will be performed to compare the incidence PAN in the placebo and treatment groups
  - As the most important outcome measure is the nominal measure of whether neuropathic pain develops after ablation, we will collect dichotomous data (neuritic vs. no-neuritic pain). We will perform McNemar's Test to test for a difference in proportions across paired samples (each patient providing his/her own control through unilateral injections of steroid and placebo-saline into each side). We will consider a p-value of less than 0.05 as significant.
  - We will collect a total of 732 samples, where each sample is nerve(s) lesioned on one side; i.e. for a patient receiving a two-level ablation bilaterally, the patient will provide a total of two samples (one experimental-steroid, one placebo-saline). Because we will only collect data from patients with bilateral injections, each acting as his/her own control, the total 732 samples will be comprised of 366 participants for each experimental/placebo condition. We plan to enroll 120 patients at Johns Hopkins and 246 from our collaborating sites in order to get total of 366 participants for each experimental/placebo condition.
  - The sample size was derived through a power-analysis calculation using G\*Power Software (ver. 3.1; Heinrich-Heine Universitat). Specifically, an *a priori* test was performed for the McNemar test with a power of 0.8 and significance level of 0.05. Based on available literature (CITE), we determined that baseline incidence of neuropathic pain is 5%, and further determined that a desirable effect size is a minimum of 50% decrease in incidence with steroid injection (overall incidence of 2.5%). With these values, the contingency table showed an odds ratio of 0.487, and the probability of discordant pairs was 0.0725, leading to a total sample size of 732 (actual power 0.82).
- d. Early stopping rules.
  - study will also be terminated if there appears to be greater than expected (>10%) incidence of PAN in the treatment group during interim analyses

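### Does the single-level recording rule for unclear neuritis turn two-sided cases into one-sided ones and distort the McNemar comparison?

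*Combined protocol and SAP*

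**What the plan says.** Section 6 (Study Statistics), item a, gives the primary outcome as "Presence of post-ablation neuritis at each lesion site". Item c then sets the unit for McNemar's test as one sample per side, "where each sample is nerve(s) lesioned on one side", with a dichotomous result (neuritic or not). Its example is that "for a patient receiving a two-level ablation bilaterally" the patient supplies two samples, one steroid and one saline. The plan counts 366 such pairs.

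Study Procedures, item b, gives opposite sides opposite treatments. Where neuritis is generalized or of unclear level, "post-ablation neuritis will be recorded at a single level that most closely matches the clinical presentation"; side is not mentioned.

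The word level is used in two ways. The injection is described as "with 1mL given at each lesion site" in Study Procedures and as "with 1 mL given at each level" in section 5, which suggests that a level may be one injection site. The two-level bilateral example uses level as a spinal level that has two sides.

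For outcome collection, questionnaires are "reviewed by co-investigators when data collection occurs", and where a clinic visit is not possible "co-researchers will follow up with patients by phone". Item d of Study Procedures declares the trial double-blind, naming the provider who performs the procedure or sees the patient in follow-up, and the patient. It gives the side directions to an un-blinded co-investigator.

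**The concern.** Each patient is his or her own control, so the side on which an event is recorded decides the arm to which it counts. A rule that reduces a diffuse complaint to one entry without mentioning side could discard half of a two-sided event. McNemar's test ignores ties and uses only discordant pairs, of which about 27 are expected in 366. A tie recorded as discordant adds a pair that carries no treatment information, and this dilutes the odds ratio. If the side were chosen by someone who knew the allocation, the error could also be directional and bias the result. The move from a per-site outcome to a per-side sample adds to the unease, because no sentence says how findings at several sites on one side become one yes/no.

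**Working it through.** **Inputs.** From section 6c: saline-side incidence ps = 0.05, steroid-side incidence pt = 0.025, 366 pairs, significance at p < 0.05. The plan names neither the version of McNemar's test nor its sidedness; the exact two-sided test is assumed here. The within-patient correlation rho and the share f of two-sided cases that are unclear are not in the documents; both are assumed and varied.

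**The plan's own figures.** With independent sides:
- saline side only: 0.05 × 0.975 = 0.04875
- steroid side only: 0.025 × 0.95 = 0.02375
- discordant: 0.04875 + 0.02375 = 0.0725; odds ratio: 0.02375 / 0.04875 = 0.487

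Both match section 6c, so the plan assumes independent sides. Expected discordant pairs: 366 × 0.0725 = 26.5. Both sides affected: p11 = 0.05 × 0.025 = 0.00125, or 366 × 0.00125 = 0.46 patients.

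**Effect of single-side recording (adverse reading).** In general p11 = ps·pt + rho·√[ps(1−ps)·pt(1−pt)], with discordant cells ps − p11 and pt − p11. Assigning unclear two-sided cases to a side at random adds f·p11/2 to each discordant cell. At rho = 0 and f = 1, the discordant rate becomes 0.0725 + 0.00125 = 0.07375 and the odds ratio (0.02375 + 0.000625) / (0.04875 + 0.000625) = 0.494. The risk difference stays at 0.025. Power is the exact rejection probability summed over Binomial(366, discordant rate):

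| rho | two-sided patients | ties kept | f = 10% | f = 50% | f = 100% |
|---|---|---|---|---|---|
| 0 (the plan) | 0.46 | 0.350 | 0.350 | 0.348 | 0.345 |
| 0.1 | 1.70 | 0.384 | 0.382 | 0.372 | 0.360 |
| 0.2 | 2.95 | 0.427 | 0.422 | 0.401 | 0.377 |
| 0.4 | 5.44 | 0.546 | 0.531 | 0.476 | 0.419 |

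The rule applies only to generalized or unclear cases, so the last column is an upper bound on the loss: it treats every two-sided case as unclear.

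**Type I error (5% on both sides, random side, f = 100%).** 0.033, 0.032, 0.032 and 0.031 at rho = 0, 0.1, 0.2 and 0.4, all below 0.05.

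**Worst case for bias.** Same null, but every unclear two-sided case assigned to saline (f·p11 added to the saline cell only):

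| rho | f = 10% | f = 50% | f = 100% |
|---|---|---|---|
| 0 | 0.033 | 0.033 | 0.035 |
| 0.1 | 0.032 | 0.036 | 0.050 |
| 0.2 | 0.031 | 0.044 | 0.086 |
| 0.4 | 0.032 | 0.084 | 0.243 |

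Under independence the error stays below 0.05 even here. Exceeding it clearly takes strong correlation, many unclear cases and wholly one-directional assignment, all at once.

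**Reading the text.** Section 6c puts two levels on one side into one sample and counts the two sides separately. Level and side are therefore different things in the statistical section, and the single-level rule, which addresses uncertainty about level, removes no information about side. One-sided multi-level cases give the same yes/no on either reading. The two sides are also lesioned at least one week apart and the onset of neuritis is recorded, which can help to attribute symptoms to a side.

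**The case for a change.** The strongest case is that the ambiguity is real and side decides the arm. No passage says that side is recorded, that both sides may be positive, or how sites combine into a side. With some 27 informative pairs, each attribution counts, and choosing the closest match is a judgement that should be made blind. Item d of Study Procedures does not expressly extend blinding to the 2-week call, other phone follow-up or questionnaire review, nor does it bar holders of the side directions from those tasks. A few sentences would settle all this.

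The omissions stand as omissions. They do not lead to a different analysis. A dichotomous result for the nerves lesioned on one side has one natural meaning, any neuritis on that side, and the site/side difference needs no more than that. A sensitivity analysis contrasting best match with both sides positive has no clear favourite. If 10% of one-sided cases are unclear (assumed, independent sides), both-sides-positive gives power 0.314, while best match gives 0.285, 0.310 or 0.337 at 50%, 70% or 90% accuracy, with break-even at about 73%.

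The blinding point is narrower than it looks, because clinic follow-up is covered by the declared double-blind design. What remains concerns callers and chart reviewers. It is a question about blinding that would exist whatever the recording rule said. The low baseline power of 0.35 is likewise another matter, arising from 366 rather than 732 pairs, and lends this point no weight.

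**Conclusion.** No change follows: this is missing detail that an analyst fills sensibly from section 6c. On the reading that section supports, the single-level rule causes no miscount. On the adverse reading, with the plan's independent sides, at most 0.46 of 366 patients are affected, power falls by about half a percentage point (0.350 to 0.345) even if every two-sided case is unclear, and the type I error stays near 0.033. At an assumed correlation of 0.2 the loss is 0.427 to 0.422 if 10% of two-sided cases are unclear, and 0.427 to 0.377 as the upper bound.

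These figures assume the exact two-sided test, incidences of 5% and 2.5%, and side assigned without knowledge of treatment. The last condition is declared for clinic follow-up but not spelled out for phone calls and questionnaire review. The conclusion would weaken if the sides proved strongly correlated, most two-sided cases were unclear, and attribution favoured one arm; the documents give no sign of that combination.
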